9.2. Statistical methods

The primary outcome variable is change in log retinal thickness at 12 weeks. A linear regression model fitted with generalized estimating equations¹³² will be used to compare the change in log retinal thickness between each of intravitreal methotrexate and ranibizumab with dexamethasone. The mean structure will include treatment effects, a time indicator for weeks 4, 8, 12, 16, 20, and 24, and time-by-treatment interaction terms. The interaction term for 12 weeks represents the difference in change in log retinal thickness from baseline. An unstructured or Toeplitz covariance matrix will be used to model the longitudinal, within-eye repeated measures and the bootstrap will be used to adjust the standard errors to account for the between-eye correlation. Other continuous and binary outcomes will be modeled in a similar manner using linear and logistic models, respectively. In addition, the models will be adjusted for the stratification variable used during randomization (presence or absence of concomitant systemic corticosteroid and/or immunosuppressive therapy).

Kaplan Meier curves will be plotted to graphically portray the cumulative percent with improvement of ME based on OCT central subfield assessment over time for the three treatments. Cox proportional hazards models taking into account the correlation between eyes

through a random effect (also known as a frailty model) will be used to compare the time to improvement of ME for the three treatment arms. Additional time-to-event outcomes (e.g. time to resolution, failure, and relapse) will be analyzed in a similar manner.

The rates of adverse events will be compared using a Negative Binomial model with a random effect for individual. The overall burden and timing of serious adverse events will be displayed graphically by plotting a single line for each individual highlighting the start and stop dates of SAE sorted by the time of first event¹³³. Robust standard errors will be computed for all analyses using statistical program-based approaches or the bootstrap, where the unit of analysis is the individual. In addition, the models will be adjusted for the stratification variable used during randomization (presence or absence of concomitant systemic corticosteroid and/or immunosuppressive therapy). All primary analyses will be according to treatment assignment (i.e. following the principles of Intention to Treat). A sensitivity analysis of based upon treatment received will be performed for comparison. Additional sensitivity analyses will be performed to assess the impact of missing data. These include 'best' and 'worst' case single imputations as well as multiple imputation and pattern mixture approaches^{134, 135}.

10. Efficacy monitoring and stopping guidelines

The guidelines for the interim efficacy analyses were developed by the Data and Safety Monitoring Committee (DSMC) and MUST Executive Committee. Additional unplanned efficacy analyses will be done if recommended by the DSMC or MUST Executive Committee.

A single pre-planned interim efficacy analysis will be performed once 40% of participants have completed the 12-week visit (the primary outcome time-point). The type I error for each of the co-primary comparisons is 0.025, i.e. half was allocated to each comparison to control the study wide type I error rate. For each comparison, the type I error thresholds would be 0.00016 at the interim analysis and 0.02484 at the final analysis to maintain a global 0.025 error rate over the course of the trial based upon O'Brien-Fleming boundaries.

11. Regulatory and ethical issues

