3.5. Secondary outcomes

- Rates of IOP elevation of ≥ 24 mm Hg, ≥ 30 mm Hg, and ≥ 10 mm Hg from baseline during the 24 weeks of follow-up
- Percent change in macular thickness as measured by OCT over the 24 weeks of follow-up
- Proportion of eyes with macular edema events over the 24 weeks of follow-up
 - $\geq 20\%$ reduction in macular thickness (or normalization of macular thickness even if there is $<20\%$ reduction)
 - "Resolution", defined as normalization of the macular thickness, i.e., <260 μm on the standard scale Worsening defined as a 20% increase in macular thickness from the lowest value after an injection
 - "Recurrence" defined as $>20\%$ increase in the central subfield measurement on OCT to an abnormal value in an eye that previously had resolution of ME
- Mean change in BCVA over the 24 weeks of follow-up.
Best-corrected visual acuity score will be measured at every study visit under standardized lighting conditions by certified study examiners masked to study treatment using logarithmic (ETDRS) visual acuity charts, according to the method described by Ferris, et al.¹²⁷
- Safety outcomes including elevated IOP (>30 mm Hg thresholds); vitreous hemorrhage; retinal tear/detachment; endophthalmitis; severe vision loss (≥ 15 Early Treatment Diabetic Retinopathy Study [ETDRS] letters) during the 24 weeks of follow-up.

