3.6. Eligibility criteria

Inclusion criteria:

Patient level inclusion criterion

1. 18 years of age or older;

Eye level inclusion criteria - at least one eye must meet all of the following conditions

2. Inactive or minimally active non-infectious anterior, intermediate, posterior or panuveitis, as defined by SUN² criteria as $\leq 0.5+$ anterior chamber cells, $\leq 0.5+$ vitreous haze grade and no active retinal/choroidal lesions for a minimum of 4 weeks;
3. Macular edema (ME) defined as the presence of macular thickness greater than the normal range for the OCT machine being used (see cut points below), regardless of the presence of cysts, following most recent intravitreal corticosteroid injection (≥ 4 weeks following intravitreal triamcinolone injection or ≥ 12 weeks following intravitreal dexamethasone implant injection);

*Greater than 300 μm for Zeiss Cirrus
Greater than 320 μm for Heidelberg Spectralis
Greater than 300 μm for Topcon 3DOCT*

4. Best corrected visual acuity (BCVA) 5/200 or better;
5. Baseline intraocular pressure > 5 mm Hg and ≤ 21 mm Hg (current use of ≤ 3 intraocular pressure-lowering medications and/or prior glaucoma surgery are acceptable (*Note: combination medications, e.g., Combigan, are counted as two IOP-lowering medications*));
6. Media clarity and pupillary dilation sufficient to allow OCT testing and assessment of the fundus.

Exclusion criteria:

Patient level exclusion criteria

1. History of infectious uveitis in either eye;
2. History of infectious scleritis of any type in either eye (*Note: History of noninfectious scleritis that has been active in past 12 months is an eye-level exclusion –see #13 below*);
3. History of keratitis (with the exception of keratitis due to dry eye) in either eye;
4. History of central serous retinopathy in either eye;
5. Active infectious conjunctivitis in either eye;
6. Oral prednisone dose > 10 mg per day (or of an alternative corticosteroid at a dose higher than that equipotent to prednisone 10 mg per day) OR oral prednisone dose ≤ 10 mg per day at baseline that has not been stable for at least 4 weeks (*note: if patient is*

off of oral prednisone at baseline (M01 study visit) dose stability requirement for past 4 weeks does not apply);

7. Systemic immunosuppressive drug therapy that has not been stable for at least 4 weeks (*note: use of systemic methotrexate is acceptable as long as regimen has been stable for at least 4 weeks*);

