9.1. Sample size, power and detectable differences

The study is powered to test whether intravitreal methotrexate and ranibizumab are each superior to intravitreal dexamethasone in terms of change in central subfield thickness. A Bonferroni correction is used to adjust for the co-primary hypotheses, i.e. a two-sided type I error rate of $0.05/2 = 0.025$ will be used to determine statistical significance. The primary outcome, retinal thickness, is measured on the log-scale, which translates to an assessment of relative change compared to baseline. The expected percent reduction in retinal thickness from baseline for dexamethasone is 25% ($\log [0.75] = -0.2877$); macular edema that persists after corticosteroid treatment is expected to be less likely to benefit from additional corticosteroid therapy. We expect the novel treatment arms to produce a reduction of 38% ($\log [0.62] = -0.4780$). A sample size of 79 independent eyes per treatment group, i.e. 79 individuals with one eye for each individual, will provide 91% power to demonstrate an improvement in the percent reduction in retinal thickness from 25% to 38% with a two-sided type I error rate of 0.025. Assuming a between-eye correlation of 0.4, 25% bilateral disease, and a 10% loss to follow-up, we need to enroll 80 individuals in each treatment arm (240 total), 8 fewer participants per arm than would be required if only one eye was included for individuals with bilateral disease after adjusting for loss to follow-up.

We also will compare the percent change in retinal thickness for intravitreal injections of methotrexate and ranibizumab; however, the percent change is expected to be similar for these therapies and the study is not powered to detect equivalence. The calculation presented here is meant to demonstrate the type of difference that would be detectable with the sample required for the primary hypotheses. As noted above, we assume that the reference group will have a percent reduction of 38% ($\log [0.62]$) with a standard deviation for the change in log-retinal thickness of 0.33. A sample size of 79 independent eyes per treatment group (the equivalent of 80 individuals per arm assuming 10% loss to follow-up, 25% bilateral disease and between-eye correlation of 0.4) provides 80% power to detect a difference between the reference percent change of 38% and a percent change of 46.6% ($\log [0.534]$) with a two-sided type I error rate of 0.05.

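### The primary 12-week contrast is a change score with the baseline slope fixed at 1: valid, but it leaves unused whatever precision baseline log thickness can add

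*Combined protocol and SAP*

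**What the plan says.** Section 9.2 makes change in log retinal thickness at 12 weeks the primary outcome variable and fits a linear model by generalized estimating equations. On the mean model: "The mean structure will include treatment effects, a time indicator for weeks 4, 8, 12, 16, 20, and 24, and time-by-treatment interaction terms". Time indicators are listed only for post-baseline weeks, so baseline is the reference visit. The treatment effects are then arm-specific baseline means. On the primary contrast: "The interaction term for 12 weeks represents the difference in change in log retinal thickness from baseline". On the covariance: "An unstructured or Toeplitz covariance matrix will be used to model the longitudinal, within-eye repeated measures", with a bootstrap for the between-eye correlation.

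The only covariate is the randomization factor: "the models will be adjusted for the stratification variable used during randomization". Baseline thickness is not a covariate, and baseline means are not held equal across arms, in the primary model or in any listed sensitivity analysis. Other continuous outcomes are to be modelled in the same way.

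Section 9.1 plans on the same footing, with a "standard deviation for the change in log-retinal thickness of 0.33" and, for each co-primary comparison, "a two-sided type I error rate of $0.05/2 = 0.025$ will be used to determine statistical significance".

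**The concern.** A change score assumes that two eyes differing by some amount in log thickness at baseline are expected to differ by the same amount at week 12. That is the same as assuming an equal expected percent reduction at every starting thickness.

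The documents give reason to doubt this. Section 3.6 admits eyes only just above normal: "Macular edema (ME) defined as the presence of macular thickness greater than the normal range for the OCT machine being used", which means above 300 µm on two of the listed machines. The planned reductions of 25% and 38% would take a 301 µm eye to about 226 µm and 187 µm (301 × 0.75 and 301 × 0.62). Section 3.5 itself provides for eyes with little room to fall, since improvement is a reduction of at least 20% "or normalization of macular thickness even if there is" a smaller one. Eyes entering near normal should therefore show smaller percent changes, which means a slope below 1.

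If the slope is not 1, estimating it targets the same treatment effect with a smaller standard error. Baseline thickness costs nothing extra: it is needed for eligibility, and baseline data are keyed before randomization (3.7). It is not a stratification factor, so chance imbalance in it is not limited by design. The point concerns both co-primary comparisons and the continuous secondary outcomes, such as BCVA.

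**Working it through.** **Inputs from section 9.1.** Reductions of 25% and 38%; SD of change 0.33 (stated in the paragraph on methotrexate versus ranibizumab); 79 independent eyes per arm; two-sided alpha 0.025; stated power 91%.

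**Planned power.**
- Difference: log(0.75) − log(0.62) = −0.2877 + 0.4780 = 0.1904.
- SE = 0.33 × √(2/79) = 0.0525, so difference/SE = 3.625.
- Power = Φ(3.625 − 2.241) = 91.7%, or 91.2% with the t distribution. The stated 91% reproduces.

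**What the 9.2 model estimates.** The stated mean structure was fitted by generalized least squares to simulated complete data (72 eyes per arm, 7 visits, three covariance matrices including a Toeplitz one, with and without the stratum). In all six fits the week-12 interaction equalled the raw difference in mean change (0.06999). The covariance choice does not recover the baseline information. With SDs of 0.33 and r = 0.5, removing the arm main effects, so that the arms share one baseline mean, cut the SE from 0.0550 to 0.0477, or 13%.

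**Gain from estimating a common slope.** Let r be the correlation of baseline with week-12 log thickness and k = SD(week 12)/SD(baseline). Both are assumptions. The slope is kr. With the SD of change held at 0.33:

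variance ratio v = k²(1 − r²) / (1 + k² − 2rk); power = Φ(3.625/√v − 2.241); eyes for the planned precision = 79v, rounded up.

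| k | r | slope | v | power | eyes per arm |
|---|---|---|---|---|---|
| 1 | 0.3 | 0.30 | 0.65 | 98.8% | 52 |
| 1 | 0.5 | 0.50 | 0.75 | 97.4% | 60 |
| 1 | 0.7 | 0.70 | 0.85 | 95.5% | 68 |
| 1 | 0.9 | 0.90 | 0.95 | 93.0% | 76 |
| 0.8 | 0.3 | 0.24 | 0.50 | 99.8% | 40 |
| 0.8 | 0.5 | 0.40 | 0.57 | 99.5% | 46 |
| 0.8 | 0.7 | 0.56 | 0.63 | 99.0% | 50 |
| 1.25 | 0.3 | 0.375 | 0.78 | 96.8% | 62 |
| 1.25 | 0.5 | 0.625 | 0.89 | 94.5% | 71 |
| 1.25 | 0.7 | 0.875 | 0.98 | 92.2% | 78 |
| 1.25 | 0.8 | 1.00 | 1.00 | 91.7% | 79 |

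**Chance imbalance.** The change score leaves (1 − slope) times the baseline difference in the contrast. At k = 1, SD(baseline) = 0.33/√(2(1 − r)), so a one-SE imbalance shifts the contrast by (1 − r) × SD(baseline) × √(2/79). At r = 0.3/0.5/0.7/0.9 this is 0.031/0.026/0.020/0.012, or 16/14/11/6% of 0.190.

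**Where adjustment can fail.**
- *Pooled slope when slopes differ by arm.* Assume slopes of 0.9 and 0.9 in the compared arms and 0.3 in the third, baseline SD 1, residual SD 0.4. The pooled slope is about 0.7. Residual variance in the compared arms is 0.16 + 0.2² = 0.20, against 0.16 + 0.1² = 0.17 for the change score, a ratio of 1.18. Simulation (20,000 runs, 79 independent eyes per arm) gives 1.18 for the pooled slope and 0.95 for arm-specific slopes.
- *Constant-variance Toeplitz with a common baseline mean.* At k = 1.25 and r = 0.7 it imposes slope b = 0.7 instead of 0.875. The ratio is (k² − 2bkr + b²)/(1 + k² − 2kr) = (1.5625 − 1.225 + 0.49)/0.8125 = 1.02.

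**The case against.** The plan is coherent. Outcome, contrast and sample size all use change, and power is adequate. The documents give neither r nor k, and the evidence for a slope below 1 is indirect: an entry cut-off and a clause in a secondary definition. Truncating baseline at the cut-off also narrows its SD, which pushes k up, towards the part of the table with little gain. All this stands, and it is why the gain is given as a range that includes zero.

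The imbalance figures are not a second benefit. At k = 1 the squared shift over the squared SE is (1 − r)/2, exactly 1 − v. That variation is already inside the planned SE. This is correct: the figures show the same gain for a given imbalance, and they are not bias.

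A floor near normal could itself make slopes differ between arms, so the common-slope table may not apply and a pooled slope could do harm. This also stands, and it shapes the choice of model in the fix.

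Section 1.7 prefers percent change because it does not depend on the OCT machine. With an estimated slope, (1 − slope) of a multiplicative machine offset stays in the residual. Randomization keeps this from biasing the comparison, but it is noise that could offset part of the gain.

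Finally, the ratios assume complete data and independent eyes, whereas 9.1 expects 10% loss and 25% bilateral disease, and nothing in the documents sizes the gain for BCVA. These points limit the precision of the figures. They do not change the finding that baseline thickness is used only with a fixed slope.

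**Conclusion.** The concern holds, as a matter of efficiency only. The planned contrast is valid and its power calculation reproduces. It fixes the baseline slope at 1, and no listed analysis relaxes that. With a common slope, estimating it cannot increase the large-sample variance. Over the assumed values of r and k the variance ratio runs from 0.50 to 1.00 and power from 99.8% to 91.7%. The gain is nil if the slope is exactly 1, and a poorly chosen adjustment can lose precision. The change is worth making because it uses a value every eligible eye already has, keeps the estimand and needs no further patients. Confidence in the size of the gain is moderate at best, since it rests on r and k, which the documents do not give.

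**What to change.** Name one model in section 9.2, choosing between:

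- **Baseline as covariate.** Model log thickness at weeks 4 to 24 on treatment, visit, treatment by visit, baseline log thickness, baseline by visit, and the stratum. If slopes may differ by arm, which the floor near normal makes plausible, allow arm-specific baseline slopes with baseline centred at the overall mean.
- **Common baseline mean.** Keep weeks 0 to 24 as the response, drop the treatment main effect, and specify an unstructured covariance, not Toeplitz. One covariance matrix for all arms still implies one slope per visit, so this version suits slopes thought to be similar across arms.

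In either case keep the week-12 treatment contrast as primary, with bootstrap standard errors that resample individuals. Report the exponential of the contrast as the ratio between arms of geometric-mean week-12-to-baseline thickness ratios (planned 0.62/0.75 = 0.827). Treat BCVA in the same way on its own scale.

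The cost is a short paragraph fixing the mean model, the covariance and the reported contrast, plus the same model in the interim analysis of section 10. No new data are needed. The change must be dated before those making it see comparative efficacy results, including that interim. If that is no longer possible, keep the planned primary analysis and report the adjusted model as a labelled sensitivity analysis.

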The safety and efficacy of ranibizumab for the treatment of patients with diabetic macular edema and macular edema due to retinal vein occlusion have been demonstrated in clinical trials which led to US FDA approval for these indications.^{106, 107} Two multicenter randomized double-masked sham injection-controlled clinical trials in adult patients with diabetic macular edema showed a significant improvement in best corrected visual acuity at 24 months in the ranibizumab-treated group compared to the group receiving sham injections. Mean change in central foveal thickness also was significantly better in ranibizumab-treated patients, with a mean decrease of 255 µm in central foveal thickness at 24 months in the ranibizumab group, compared with a 130 µm decrease in the sham injection group (P < 0.0001). Less than 5% of patients experienced an ocular adverse event, such as endophthalmitis, retinal detachment or vitreous hemorrhage, by 24 months. Ranibizumab also is approved for the treatment of macular edema following branch retinal vein occlusion.^{108, 109} A phase III multicenter, randomized,

double-masked, controlled study followed by a 6-month observation period showed a significant improvement in best corrected visual acuity (18.3 letters from baseline) compared with the sham injection group (7.3 letters, $P < 0.0001$). A significant improvement in central foveal thickness also occurred in the ranibizumab group (decrease of 345 μm at 6 months), compared with the sham injection group (158 μm decrease, $P < 0.001$). The safety profile of ranibizumab was consistent with prior phase III clinical trials of ranibizumab in neovascular age-related macular degeneration, with a very low rate of endophthalmitis, retinal tear/detachment and arterial thromboembolic events. A second phase III trial on vein occlusion enrolled patients with macular edema following central retinal vein occlusion and showed similar efficacy and safety as the trial evaluating branch retinal vein occlusion.^{110, 111}

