3.1. Type of study

- Randomized, three-arm, parallel design, randomized comparative effectiveness trial
- Randomization stratified by presence or absence of concomitant systemic corticosteroid and/or immunosuppressive therapy for any indication
- Unit of randomization is patient, not eye; if both eyes meet eligibility criteria, both receive same treatment
- Allocation ratio (1:1:1)
- Multicenter
- Fixed sample size, 240 (80 per treatment group)
- Anniversary close-out at the 6-month clinic visit
- Reading center graders and visual acuity examiners will be masked to treatment
- Treating physicians and patients will be unmasked (the intravitreal therapies are different in appearance and have potentially different injection schedules)

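### Section 9.2 requires robust or bootstrap standard errors for all analyses and has no rule for zero-event arms, where the usual Wald use of them gives falsely significant safety differences

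*Combined protocol and SAP*

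**What the plan says.** Section 9.2 sets the adverse-event method in one sentence: "The rates of adverse events will be compared using a Negative Binomial model with a random effect for individual". Shortly after comes a rule without exceptions: "Robust standard errors will be computed for all analyses using statistical program-based approaches or the bootstrap, where the unit of analysis is the individual". For secondary outcomes that are not counts it says: "Other continuous and binary outcomes will be modeled in a similar manner using linear and logistic models, respectively".

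Among the safety outcomes in section 3.5 are "vitreous hemorrhage; retinal tear/detachment; endophthalmitis; severe vision loss", assessed "during the 24 weeks of follow-up". Section 7.4 classes endophthalmitis, retinal tear or detachment and vitreous hemorrhage as rare and serious. Section 3.1 fixes 80 patients per arm. The nearest rate for these ocular events is in section 1.6, from the ranibizumab trials in diabetic macular edema: "Less than 5% of patients experienced an ocular adverse event, such as endophthalmitis, retinal detachment or vitreous hemorrhage, by 24 months".

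No section gives an exact, score, penalised, descriptive-only or minimum-count rule for sparse events.

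**The concern.** When one arm has no events, the maximum-likelihood log rate in that arm has no finite value. The software pushes it towards minus infinity and stops at its tolerance. A model-based standard error grows with it, so the test correctly shows no information. A sandwich standard error is built from residuals. In an empty arm these are almost zero, so the standard error stays small while the estimate runs away, and their ratio is then very large and means nothing.

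At stake is the tolerability half of the objective in section 2.1. A single endophthalmitis in one arm and none in another could be reported as decisive evidence against the first. Section 11.2 also has the DSMC reports formally compare adverse events by arm, at times when counts are smaller still.

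**Working it through.** **The plan's own figure.** No event count, power or significance level is stated for adverse events. The check uses only the 80 per arm, and the basis of that number reproduces: with "25% bilateral disease, and a 10% loss to follow-up" and a between-eye correlation of 0.4, 80 × 0.9 × (0.75 + 0.25 × 2/1.4) = 79.7 effective eyes, against the 79 required.

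**Step 1: how likely is an empty arm?** Take 5% at 24 months (104.3 weeks) as the ceiling and assume a constant hazard and the same rate in all arms. The 24-week rate is then p = 1 − 0.95^(24/104.3) = 0.0117. With q = (1 − p)^n, the chance that at least one of three arms is empty is 1 − (1 − q)^3, and that exactly one arm of a pair is empty is 2q(1 − q).

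| 24-week rate | n per arm | Given arm empty | Any of three empty | Exactly one of a pair empty |
|---|---|---|---|---|
| 1.17% (ceiling for the group of events) | 80 | 0.39 | 0.77 | 0.48 |
| 1.17% | 72 (10% lost) | 0.43 | 0.81 | 0.49 |
| 0.4% (assumed, single event type) | 80 | 0.73 | 0.98 | 0.40 |
| 5% (assumed, for contrast) | 80 | 0.02 | 0.05 | 0.03 |

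**Step 2: sandwich standard error, GLM.** In a two-arm Poisson model, an arm with k of n patients affected contributes 1/k − 1/n to the robust variance of the log rate ratio. An empty arm contributes nμ²/(nμ)² = 1/n, however small μ becomes. The sum is 1/k, so the robust SE is 1/√k.

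| Events, 80 v 80 | Log rate ratio at convergence | Robust SE | Robust p | Model-based p | Fisher p |
|---|---|---|---|---|---|
| 0 v 1 | −20.4 | 1.00 | about 10^-92 | 0.999 | 1.00 |
| 0 v 2 | −20.4 | 0.71 | about 10^-182 | 0.999 | 0.50 |
| 0 v 3 | −21.4 | 0.58 | below 10^-270 | 0.999 | 0.25 |

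Poisson and negative binomial (dispersion 1) agree. Logistic regression gives p of about 10^-88 for 0 v 1. As a control, 1 v 2 events gives SE = √(1 − 1/80 + 1/2 − 1/80) = 1.21, z = 0.693/1.21 = 0.57 and p = 0.57, so the fault lies in the empty arm.

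**Step 3: the specified mixed model, 0 v 1.** Six visits per patient were assumed. The dispersion (a) and the SD of the random effect (s) are also assumptions. The robust SE is 1.00 to 1.02 throughout, and p depends on where iteration stops in the empty arm:

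| Empty-arm linear predictor | a = 0.5, s = 0.5 | a = 1, s = 1 | a = 2, s = 1.5 |
|---|---|---|---|
| −10 | 0.0002 | 0.0009 | 0.008 |
| −15 | 3 × 10^-18 | 9 × 10^-17 | 4 × 10^-14 |
| −18 | 1 × 10^-31 | 1 × 10^-29 | 1 × 10^-25 |

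The model-based p on the same data is 0.50 to 0.97. The random effect does not remove the problem.

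**Step 4: bootstrap over individuals, 0 v 1.** A resample of 160 patients misses the one event with probability (1 − 1/160)^160 = 0.37, and both arms are then empty. If these resamples are dropped, SE = 0.43 and z is about −47. If they are kept as no effect, SE is about 20.4 × √(0.63 × 0.37) = 9.8, z is about −2.1 and p about 0.04. For 0 v 3, dropping gives p near 0 and keeping gives about 2 × 10^-6.

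**Step 5: false-positive rate.** With equal true rates of 1.17% and a nominal 0.05 level, the GLM sandwich test rejects in about 48% of pairwise comparisons, essentially whenever exactly one arm is empty. Fisher's test rejects in about 0.03%.

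**The case against.** Several objections stand and limit the point.

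- **No test is named.** Section 9.2 asks for robust standard errors, not Wald tests, and sets no significance level for adverse events. A reader might infer that Wald tests are prescribed. That is the ordinary use of such a standard error, but it remains an inference.
- **Not every comparison is affected.** Section 1.6 quotes a peak of 7.1% with IOP of 25 mm Hg or more on the 0.7 mg implant. That is 0.071 × 80 = 5.7 expected patients, and an empty arm has probability 0.929^80 = 0.003. Overall adverse-event counts will not be sparse either.
- **The rate is indirect.** The 5% is an upper bound for a group of events, in another disease and for one of the three drugs. It makes empty arms likely under the stated assumptions but does not prove them.
- **The most extreme p-values belong to the GLM.** The specified mixed model gives 0.008 to 10^-31, and the bootstrap can give 0.04. A percentile interval that keeps empty resamples would reach the null for 0 v 1, 0 v 2 and 0 v 3, but the plan speaks only of standard errors.
- **An analyst might notice.** A rate ratio near 10^-9 is conspicuous, and some programs report non-convergence or no standard error. The fallback would then be chosen after the data are seen, which a plan should prevent.

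None of this supplies the missing rule, and every version of the standard error examined puts 0 v 1 below 0.05.

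**Conclusion.** The point holds as a defect in the analysis of rare safety events. The required standard errors are unsuitable when an arm is empty, and section 9.2 offers nothing else. At the 1.2% ceiling, about half of pairwise comparisons (0.48) would have exactly one empty arm. A Wald test on the sandwich standard error would call these significant, although the exact p is 1.00 for 0 v 1 and 0.25 for 0 v 3. Rarer single event types make an empty arm more likely still.

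The probabilities rest on a constant hazard, equal rates in all arms and independent patients. The p-values rest on ordinary Wald use and on the software's stopping point. The documents do not support the wider reading that all adverse-event comparisons are invalid. The primary efficacy analysis and common events, including IOP elevation in the dexamethasone arm, are not touched. The change should be made, but it does not threaten the trial's main result.

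**What to change.** Add a paragraph to section 9.2:

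- Use the negative binomial model only for events with a pre-specified minimum number of affected participants in each compared arm, for example 5. That number is a judgement and should be fixed before the comparison is made.
- For all sparser events, including any arm with none, report participants affected per arm, counting a participant once if either study eye is affected. Give a patient-level exact test and exact confidence interval, stratified by the randomization factor if adjustment is wanted.
- State that no robust or bootstrap Wald p-value is given for these events, and apply the same rule to binary safety outcomes and to the DSMC comparisons.

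Exact limits show how little an empty arm says: for 0/80 the two-sided 95% upper limit is 1 − 0.025^(1/80) = 4.5%.

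The cost is a few lines of text and code, with no new data. The intervals are wider and slightly conservative. For the sparse events, recurrent-event counts are lost, as is the stratification adjustment if the exact test is unstratified.
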